#### **2.2.4 Inclusion of Placebo**

Placebo recipients are included in order to maintain blinding, provide safety reference data, provide controls for the immunogenicity assays, and to confirm the infectivity of the *N. americanus* Larval Inoculum (i.e., infectivity controls) during the CHHI stage of the trial.

#### **2.2.5 Clinical Development Plan for the Human Hookworm Vaccine**

The target population for the human hookworm vaccine is children less than 10 years of age living in hookworm endemic areas, since this is the age group that is most at risk of disease from this infection. Prior to conducting clinical trials in this age group, however, Na-GST-1 will be tested in healthy, hookworm-naïve adults living in area where hookworm is not endemic, to provide proof-of-efficacy before large-scale, long-duration and expensive pediatric Phase 2 and 3 field trials are undertaken in endemic areas.

The decision to proceed to Phase 2 and 3 testing in children will be taken after the Sponsor has reviewed the final clinical study report of the study described in this protocol. Phase 1 testing of Na-GST-1/Alhydrogel is currently planned to start in the third quarter of 2016 in children aged 5-10 years living in a hookworm endemic area of Gabon. After safety and immunogenicity of this product is shown in children, and if the results of the Phase 2 trial described in this protocol indicate efficacy of at least one of the Na-GST-1 formulations, further and more extensive testing will be pursued, ultimately culminating in Phase 2 and 3 trials in this target population in which protection against natural infection will be the primary endpoint.

In the first pediatric Phase 2 trial, the hookworm vaccine will be compared to a licensed comparator vaccine to evaluate the impact of mean fecal egg counts as well as a variety of clinical and parasitological endpoints. Assuming that an impact on infection is shown in the Phase 2 trial, that there are no new safety issues that arise due to co-formulation of the antigens, and that combining them into one product does not adversely affect the immunogenicity of either, this product will be tested in a pivotal multi-center Phase 3 trial in children. The primary endpoint of the Phase 3 trial will be the incidence of moderate and heavy hookworm infection (as determined by fecal egg counts) following administration of an anthelminthic and vaccination.

## 2.3 Potential Risks and Benefits

### 2.3.1 Potential Risk

Risks to subjects are those associated with venipuncture, intramuscular injection of the *Na*-GST-1 vaccine formulations, possible reactions to the vaccine formulations, possible reactions to CHHI, possible reactions to albendazole, and breach of confidentiality.

#### 2.3.1.1 Risks of Venipuncture

Risks occasionally associated with venipuncture include pain and bruising at the site of venipuncture, lightheadedness, and syncope (rarely). Intramuscular (IM) injection also may cause transient discomfort and fainting.

#### 2.3.1.2 Risks of Vaccination

Possible local vaccine reactions include pain, swelling, erythema, induration, transient limitation of limb movement, lymphadenopathy, or pruritus at the injection site. Local subcutaneous nodules, believed to be granulomatous reactions to aluminum hydroxide, have been observed with use of aluminum hydroxide-based adjuvants. Thus, most aluminum hydroxide-adsorbed vaccines are injected intramuscularly rather than subcutaneously. Systemic reactions such as fever, headache, malaise, myalgia, and joint pain, may also possibly occur. Immediate hypersensitivity reactions including urticaria, anaphylaxis, or other IgE-mediated responses are possible as with any vaccine. As with any investigational vaccine, there is a theoretical possibility of risks about which we have no present knowledge. Subjects will be informed of any such risks should further data become available.

Transient, clinically insignificant decreases in white blood cell counts and platelet counts have been observed in the two weeks following receipt of other CpG ODN adjuvant preparations.

CpG 10104 is an immune activator, and has the potential to overcome the normal tolerance of the immune system for self antigens. In a number of murine models, administration of CpG ODN has been associated with development of certain autoimmune phenomenon. However, the relevance of this finding to humans is unclear because while TLR9 receptors are widely distributed among immune cells in mice, they appear to be restricted to B cells and plasmacytoid dendritic cells in humans. No subject in any study to date with CpG 7909 oligonucleotides, a closely related CpG sequence to CpG 10104, has developed signs or symptoms of autoimmune disease.

In animal studies, CpG ODN given by themselves only rarely induce the production of anti-double-stranded DNA antibodies. However, if the CpG 7909 ODN is administered as a complex together with a foreign protein or other antigen that can elicit T cell help, then it is likely that antibodies against the CpG 7909 ODN will be produced, and these may cross-react with double-stranded DNA. Vaccination of humans with a CpG 7909 ODN together with an antigen capable of binding to the ODN could be expected to result in the production of IgG anti-ODN antibodies, which could cross react with self DNA.

This phenomenon has been observed in some clinical studies with CpG ODNs involving use of CpG 7909 as an antineoplastic agent, in which study subjects have developed detectable antibody to double-stranded DNA. These antibodies have generally declined to baseline after cessation of CpG 7909, and have not been associated with other autoimmune phenomenon, and their possible clinical significance is unknown. Subjects in the study described in this protocol will be closely monitored for laboratory evidence (e.g., anti-double stranded DNA antibodies or rheumatoid factor) or clinical signs or symptoms of autoimmunity.

Female subjects will be cautioned of the unknown risk of the Na-GST-1/Alhydrogel® vaccine administered with or without AP 10-701 or CpG 10104, and of hookworm infection (and of the albendazole used to treat hookworm infection) to the fetus. A female of childbearing potential, unless surgically sterile (i.e., bilateral tubal ligation, bilateral oophorectomy, or complete hysterectomy), at least 2 years postmenopausal, practices abstinence, or has a vasectomized partner, must practice effective contraception (including oral, intra/transdermal, intravaginal, or implanted hormonal contraceptives; intrauterine device (IUD); double barrier methods [condom plus foam or spermicide, diaphragm plus foam or spermicide], or the Essure procedure) until documented clearance of hookworm infection following treatment with albendazole. Female subjects will be counseled by a study team member, or referred to the health provider of their choice, for evaluation and institution of an appropriate contraceptive method.

Female subjects will be cautioned of the theoretical risk of albendazole during pregnancy. Per the FDA's categorization of drug risks to a fetus, albendazole is Category C, indicating that animal reproduction studies have shown an adverse effect on the fetus. However, teratogenicity in humans has not been observed, and a study of over 800 women treated with albendazole during the second and third trimesters demonstrated no adverse effects (70). Use in the first trimester, however, is still not recommended, but potential benefits may warrant use of the drug in pregnant women despite potential risks. Albendazole has been shown to cause embryotoxicity and skeletal malformations in pregnant rats and rabbits. Female subjects will be counseled on the potential risks of albendazole use during pregnancy at each weekly visit.

### **2.3.1.3 Risks of Experimental Infection with *N. americanus* Larval Inoculum**

Expected adverse effects of being inoculated with *N. americanus* infective larvae are local skin reactions at the site of application of the larvae and gastrointestinal symptoms upon maturation of the parasites into adult hookworms in the small intestine of the host. Reported skin reactions include localized maculopapular or papulovesicular rash that may be significant and prolonged (up to a month) when higher doses ( $\geq 50$ ) of larvae are applied. Occasional respiratory symptoms may be experienced during the migration of larvae through the lungs, including dry cough, shortness of breath, and wheeze. Reported gastrointestinal symptoms include abdominal bloating and pain, flatulence, diarrhea, nausea, and vomiting.

As with any investigational product, there is a theoretical possibility of risks of CHHI about which we have no present knowledge. Subjects will be informed of any such risks should further data become available during the course of this or other clinical studies. Risks associated with chronic hookworm infection include iron deficiency, iron-deficiency anemia (associated with fatigue and malaise) and chronic gastrointestinal symptoms including flatulence, abdominal bloating, abdominal pain, diarrhea, nausea, and vomiting. However, these usually only occur after several months or years of infection, which will not occur during this study.

Volunteers in this study who are experimentally infected with the *N. americanus* Larval Inoculum may develop patent infections and shed hookworm eggs in their feces. It is extremely unlikely that a bystander individual – for example, someone living in the same household as the study subject – could become infected with *N. americanus* due to exposure to these hookworm eggs that are shed, for several reasons. First, to become infectious to humans, hookworm eggs must hatch to release larvae into the environment. Hatching and development into infective larvae require a moist and warm environment (optimally between 23-33°C) and a certain period of time, generally estimated to be at least a week. Second, *N. americanus* larvae can infect humans only by coming into contact with skin; they are not infectious by oral ingestion.

Therefore, in order for a study subject to transmit their hookworm infection to another person, they would have to defecate such that their feces did not get disposed in a toilet and were incubated at a warm temperature in adequate moisture for over a week. The incubated feces would then have to come into contact with another person's skin. Since almost all residents of the Washington, DC, area have access to flush toilets, the prospect of them depositing their feces outside of a toilet and into a warm, moist environment such that the hookworm eggs could incubate and hatch is quite far-fetched. However, to prevent this extremely unlikely event from occurring, all study subjects will be counseled to practice good hygiene and to always defecate in a flush toilet and to dispose of all fecally contaminated matter immediately into a toilet.

#### **2.3.1.4 Risks of Albendazole**

Albendazole is a licensed anthelmintic medication that is used ubiquitously throughout the world to treat intestinal nematode infections. Expected adverse effects associated with administration of three daily doses of albendazole include abdominal pain, nausea, vomiting, and diarrhea.

#### **2.3.2 Precautions Taken to Minimize Risks**

In order to minimize the risk to subjects, all subjects will be monitored closely during their participation in this study. The study vaccines, AP 10-701, and CpG 10104 have been produced according to current Good Manufacturing Practices (GMP). The *N. americanus* larvae that will be used in this study have been produced according to the procedure outlined in the IND for this product. The vaccine products and *N. americanus* larvae will be administered by experienced investigators with drugs and equipment available for the treatment of anaphylaxis and other potential adverse reactions. All vaccine doses will be given by intramuscular injection to minimize injection site reactions such as pain.

Subjects will be monitored throughout their infection for the development of anemia, by means of regular complete blood counts. Any subject who develops significant anemia during the study

that meets one of the halting rules (see **Section 9.5**) will be treated with albendazole for the infection, according to the procedure outlined in **Section 7.7** of the protocol.

#### **Maintenance of Confidentiality**

Subjects will be asked to provide personal health information. All attempts will be made to keep this information confidential within the limits of the law. However, there is a chance that unauthorized persons will see the subjects' personal health information. All records will be kept in a locked file cabinet or maintained in a locked room at the study site. Electronic files will be password protected. Only people who are involved in the conduct, oversight, monitoring, or auditing of this study will be allowed access to the personal health information that is collected. Any publications from this study will not use information that will identify subjects by name.

#### **2.3.3 Known Potential Benefits**

Subjects may not receive any direct benefit from participation in this study. It is hoped that information gained in this study will contribute to the development of a safe and effective hookworm vaccine.

## 3 OBJECTIVES

### 3.1 Study Objectives

#### Primary:

1. To compare the impact of vaccination with *Na*-GST-1/Alhydrogel® delivered with or without AP 10-701 or CpG 10104 on controlled human hookworm infection (CHHI) with *N. americanus* larvae in healthy, hookworm-naïve adults, as determined by the presence of eggs using a qualified flotation technique.
2. To evaluate the safety and reactogenicity of *Na*-GST-1/ Alhydrogel® delivered with or without AP 10-701 or CpG 10104 on Days 0, 56 and 112, in healthy, hookworm-naïve adults.

#### Secondary:

1. To compare the impact of vaccination with *Na*-GST-1/Alhydrogel® delivered with or without AP 10-701 or CpG 10104 on fecal egg counts, as determined by the McMaster method, after controlled human hookworm infection (CHHI) with *N. americanus* larvae in healthy, hookworm-naïve adults.
2. To assess the relationship between antibody responses to *Na*-GST-1 induced by vaccination with *Na*-GST-1/Alhydrogel® delivered with or without AP 10-701 or CpG 10104 and responses to CHHI in healthy, hookworm-naïve adults, as determined by the presence of eggs using a qualified flotation technique.
3. To assess the duration of antibody responses to *Na*-GST-1 induced by vaccination with *Na*-GST-1/Alhydrogel® delivered with or without AP 10-701 or CpG 10104.

#### Exploratory:

1. To assess the relationship between the functional capacity of vaccine-induced antibodies that neutralize the *in vitro* activity of native *Na*-GST-1 enzyme and responses to CHHI in healthy, hookworm-naïve adults.
2. To compare the impact of vaccination with *Na*-GST-1/Alhydrogel® delivered with or without AP 10-701 or CpG 10104 on levels of hookworm DNA as detected by real-time PCR in healthy, hookworm-naïve adults challenged with CHHI, as determined by the presence of eggs using a qualified flotation technique.
3. To assess the impact of vaccination with *Na*-GST-1/Alhydrogel® delivered with or without AP 10-701 or CpG 10104 on the affinity of antibody-antigen interactions, and how affinity relates to responses to CHHI in healthy, hookworm-naïve adults, as determined by the presence of eggs using a qualified flotation technique.
4. To assess the relationship between *Na*-GST-1 specific memory B cells induced by vaccination with *Na*-GST-1/Alhydrogel® delivered with or without AP 10-701 or CpG 10104 and responses to CHHI in healthy, hookworm-naïve adults, as determined by the presence of eggs using a qualified flotation technique.

5. To assess the relationship between innate immune responses to Na-GST-1/Alhydrogel® delivered with or without AP 10-701 or CpG 10104 and responses to CHHI in healthy, hookworm-naïve adults.

## 3.2 Study Outcome Measures

### 3.2.1 Primary Outcome Measures

#### Efficacy

The following parameters will be evaluated for each formulation of Na-GST-1, in comparison to the saline placebo control:

1. Proportion of subjects with detectable hookworm eggs, at any time point, in fecal samples, as determined by microscopy using the qualified saline flotation technique.

#### Safety

The following parameters will be evaluated for each formulation of Na-GST-1, in comparison to the saline placebo control:

1. Frequency of solicited injection site and systemic reactogenicity, graded by severity, on the day of each study vaccination through 14 days after each study vaccination.
2. Frequency of solicited adverse events, graded by severity, on the day of CHHI through study Day 280.
3. Frequency of study vaccine-related Serious Adverse Events from the time of the first study vaccination through approximately 10 months after the last study vaccination.
4. Frequency of clinical safety laboratory adverse events.
5. Frequency of unsolicited adverse events, graded by severity, from the time of each study vaccination through approximately 1 month after each study vaccination; and from the time of CHHI through treatment with albendazole (Day 297).
6. Frequency of new-onset chronic medical conditions through approximately 10 months after the third study vaccination.
7. Frequency of Adverse Events of Special Interest through approximately 10 months after the third study vaccination.

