## 9 ASSESSMENT OF SAFETY

### 9.1 Specification of Safety Parameters

Safety will be assessed by the frequency and severity of:

1. Study product (vaccine or CHHI)-related serious adverse events occurring from the time of the first study vaccination through approximately 10 months after the last study vaccination.
2. Study vaccine-related solicited Adverse Events – reactogenicity events occurring on the day of each study vaccination through 14 days after each study vaccination:
  - a) Injection site reactions including erythema (redness), induration (hardness)/swelling, pain, and tenderness.
  - b) Systemic reactions including fever, myalgia (body aches/muscular pain exclusive of the injection site), arthralgia (joint pain exclusive of the injection site), headache, nausea, and vomiting.
3. CHHI-related solicited adverse events – reactogenicity events occurring on the day of CHHI through study Day 280 (time of treatment with first dose of albendazole):
  - a) Application site reactions including pruritus, rash, induration (hardness)/swelling, pain, and tenderness.
  - b) Gastrointestinal reactions including abdominal pain, abdominal bloating, flatulence, nausea, vomiting, and diarrhea.
  - c) Respiratory reactions (possibly due to migration of larvae through the lungs) including cough and sore throat.
4. Clinical safety laboratory adverse events occurring throughout the study. Parameters to be evaluated include WBC, ANC, absolute eosinophil count, hemoglobin concentration, and platelet count; ALT; creatinine; rheumatoid factor; and, anti-ds DNA antibodies.
5. Unsolicited Adverse Events – non-serious adverse events occurring from the time of each study vaccination through approximately 28 days after each vaccination and from study Day 140 (day of CHHI) through Day 297.
6. New-onset chronic medical conditions occurring from the time of the first study vaccination through approximately 10 months after the last study vaccination.
7. Adverse Events of Special Interest occurring from the time of the first study vaccination through approximately 10 months after the last study vaccination.

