## 9.2 Methods and Timing for Assessing, Recording, and Analyzing Safety Parameters

### 9.2.1 Adverse Events

An adverse event (AE) includes any noxious, pathological or unintended change in anatomical, physiological or metabolic functions as indicated by physical signs, symptoms and/or laboratory-detected changes occurring in any phase of the clinical study, whether associated with the study product (i.e., vaccine, placebo or CHHI), and whether or not considered study product related. This includes an exacerbation of pre-existing conditions and intercurrent illnesses.

All AEs will be graded for severity and relationship to study vaccine or to CHHI. A licensed clinician (i.e. physician, nurse practitioner, physician assistant) listed on the Form FDA 1572 will be readily available for the duration of the trial to assess AEs. Should a subject call on a study clinician to report an AE, it will be fully documented in their study chart, and discussed with the Principal Investigator.

All AEs will be assessed by the investigator using the following protocol-defined grading system, as or described in **Tables 1-5**:

- Grade 1: **Mild** - No effect on activities of daily living; no medical intervention/therapy required
- Grade 2: **Moderate** - Partial limitation in activities of daily living (can complete  $\geq 50\%$  of baseline); no or minimal medical intervention/therapy required
- Grade 3: **Severe** - Activities of daily living limited to  $< 50\%$  of baseline; medical evaluation/therapy required

All AEs will have their possible relationship to study vaccine or CHHI assessed using the following terms:

- Definite: Clear-cut temporal association, and no other possible cause.
- Probable: Clear-cut temporal association and a potential alternative etiology is not apparent.
- Possible: Less clear temporal association; other etiologies also possible.
- Unlikely: Temporal association between the AE and the study product or the nature of the event is such that the study product is not likely to have had any reasonable association with the observed illness/event (cause and effect relationship improbable but not impossible).
- Not Related: The AE is completely independent of study product administration; and/or evidence exists that the event is definitely related to another etiology.

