### **9.2.5 Serious Adverse Events**

An SAE is an AE, whether considered related to a study product or not, meeting one of the following conditions:

1. Death during the period of protocol-defined surveillance
2. Life threatening: defined as an event that places a subject at immediate risk of death at the time of the event and does not refer to an event that hypothetically might have caused death were it more severe
3. Hospitalization during the period of protocol-defined surveillance: defined as at least an overnight stay in the hospital or emergency ward for treatment that would have been inappropriate if administered in the outpatient setting
4. Results in a congenital anomaly or birth defect
5. Results in a persistent or significant disability or incapacity: defined as a substantial disruption of the study subject's ability to carry out normal life functions
6. Any other important medical event that may not result in death, be life threatening, or require hospitalization, may be considered a serious AE when, based upon appropriate medical judgment, the event may jeopardize the subject and may require medical or surgical intervention to prevent one of the outcomes listed above.

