- c. The proportion of subjects with detectable hookworm eggs in each of the intervention groups (Groups 1, 2 and 3) will be compared to the proportion of subjects in the placebo control group (Group 4) using a one sided Fisher exact test. The p-values from the three tests will be adjusted using the Holm-Bonferroni procedure to control the familywise error rate at 0.05. Power calculations are based on this outcome.

Primary Objective #2: To evaluate the safety and reactogenicity of Na-GST-1/ Alhydrogel® delivered with or without AP 10-701 or CpG 10104 on Days 0, 56 and 112, in healthy, hookworm-naïve adults.

AEs will be coded according to Medical Dictionary of Regulatory Activities (MedDRA™) preferred terms. The frequency, severity, and relationship of AEs per each vaccine formulation of Na-GST-1 will be presented in tabular form using the MedDRA™ coded term and organized by MedDRA™ System, Organ, and Class (SOC) designations.

1. The frequency of solicited local injection site and systemic AEs, and unsolicited AEs will be summarized by SOC and preferred term.
2. Line listings of clinical and laboratory AEs classified as solicited injection site, solicited systemic, or unsolicited and will be displayed in tables stratified by formulation group (i.e., Na-GST-1/Alhydrogel, Na-GST-1/Alhydrogel plus AP 10-701, Na-GST-1/Alhydrogel plus CpG 10104, or saline placebo).
3. AEs will be summarized by severity and relationship to vaccine by individuals and formulation of Na-GST-1.
4. The frequency of vaccine-related SAEs and AESIs will be tallied as well as summarized by body system, by vaccine formulation.

*Primary Outcome #2 Measures:*

The following summary parameters will be evaluated for each formulation of Na-GST-1, in comparison to saline placebo control:

1. Frequency of solicited injection site and systemic reactogenicity, graded by severity, on the day of each study vaccination through 14 days after each study vaccination.
2. Frequency of solicited adverse events, graded by severity, on the day of CHHI through study Day 280.
3. Frequency of study vaccine-related Serious Adverse Events from the time of the first study vaccination through approximately 10 months after the last study vaccination.
4. Frequency of clinical safety laboratory adverse events.

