### **5.2 Definition**

**Baseline:** Baseline is defined as the latest non-missing assessment (whether from scheduled or unscheduled) prior to the first dose administration of the study vaccine, unless otherwise stated.

The **Post-baseline** values are defined as measurements taken after the first administration of study product.

**Change from Baseline:** The change from baseline values will be calculated as post baseline value minus the baseline value.

**An Adverse Event** is any untoward medical occurrence in a subject or clinical investigation in a subject administered a pharmaceutical product and which does not necessarily have to have a causal relationship with this vaccination. An adverse event can be any unfavorable sign (including an abnormal laboratory finding), symptom, or disease temporally associated with the use of the investigational product, whether considered related or not related to the investigational product.

A pre-vaccination condition is any event in a clinical study subject that occurs after he/she signed the Informed Consent Form (ICF) up until the first administration of study vaccine. All pre-vaccination conditions will be considered as medical history whereas any pre-vaccination condition that worsens after vaccination will be considered as an AE.

**An SAE** is any AE that results in death, is life-threatening (this refers to an event in which the subject was at risk of death at the time of the event; it does not refer to an event that hypothetically might have caused death had it been more severe), requires inpatient hospitalization or prolongation of existing hospitalization, results in persistent or significant disability/incapacity, is a congenital anomaly/birth defect, requires medical or surgical intervention to prevent any of the occurrences noted above.

**Unexpected Adverse Event:** Any adverse event, the specificity or severity of which is not consistent with the current Investigator's Brochure.

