- Additionally, the proportion of subjects with at least one injection site AE and frequency of AEs grouped by SOC term will be compared by *Na-GST-1* vaccine formulation and placebo. The null hypotheses that the Adverse event type and number of adverse events is the same across all vaccination groups and placebo. 2-sided *p*-values will be obtained from the Fisher's exact test.

All AEs during the study will be summarized for the respective vaccination. A subject experiencing the same AE multiple times will be counted only once for that preferred term. Similarly, if a subject experience multiple AEs (preferred terms) within the same system organ class then that subject will be

counted only once for that system organ class. When summarizing by severity, only event with highest severity will be counted. All AEs will be listed in chronological order of the events occurred.

Individual subject listings containing all information pertaining to adverse events noted during the study will be presented by Vaccine Group, subject, verbatim and preferred terms, system organ class, start date, stop date, maximum severity, outcome, action taken and study vaccine relatedness.

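### The primary SAE outcome counts only vaccine-related SAEs, while Protocol 9.1 counts vaccine- or CHHI-related SAEs, and no planned output isolates the CHHI-related ones

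*Protocol*

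**What the plan says.** The primary SAE outcome appears in three places with the same scope. Protocol 3.2.1 (Safety, no. 3) has "Frequency of study vaccine-related Serious Adverse Events from the time of the first study vaccination", running to about 10 months after the last vaccination. Protocol 11.4 restates it under Primary Objective 2, and SAP 4.1 lists it as no. 4. The tabulation planned in Protocol 11.4 is equally narrow: "The frequency of vaccine-related SAEs and AESIs will be tallied as well as summarized by body system, by vaccine formulation".

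Protocol 9.1, which sets out how safety will be assessed, gives a wider scope over the same period as its no. 1: "Study product (vaccine or CHHI)-related serious adverse events occurring from the time of the first study vaccination".

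On causality, Protocol 9.2.1 says "All AEs will be graded for severity and relationship to study vaccine or to CHHI", and its definition of study product takes in vaccine, placebo and CHHI. The halting rules in Protocol 9.5 count SAEs related to either the vaccine or CHHI.

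In SAP 5.7.5.1, the overview table has rows for vaccine-related AEs, SAEs and AESIs and none for CHHI-related events. The by-relationship summary uses one axis, relationship to study product. There is a table of all SAEs by group whatever the cause, and another of vaccine-related SAEs. The AE listing ends with "maximum severity, outcome, action taken and study vaccine relatedness".

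**The concern.** Every subject who reaches Day 140, placebo recipients included, is due to receive live larvae, which are an investigational product under their own IND. The primary safety set already covers the challenge in other items: no. 2 takes solicited events from CHHI to Day 280, and no. 5 takes unsolicited events from CHHI to Day 297. Only the SAE item is confined to the vaccine. A challenge-caused SAE could therefore halt the trial under 9.5 and still add nothing to the primary SAE outcome.

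The stake is how the primary result reads. A report could state that there were no related SAEs on the primary measure, and the reader would have to find the challenge-caused event in the all-SAE table, where nothing attributes it to CHHI.

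**Working it through.** The plan gives no figure on this point, so the check compares the texts. Take one SAE judged related to CHHI and not to the vaccine, and follow it through the planned outcomes and outputs.

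1. **Protocol 3.2.1 no. 3, Protocol 11.4, SAP 4.1 no. 4:** not counted, because the scope is vaccine-related.
2. **Protocol 9.1 no. 1:** counted, because the scope is vaccine or CHHI.
3. **Outcome no. 2 (solicited events, CHHI to Day 280):** counted if it is a solicited event, though not as an SAE. SAP 5.7.5.3 tabulates these events in the Per Protocol Population, which requires completion of the study, so a subject who withdrew because of the event would be absent from that table.
4. **Outcome no. 7 (AESIs):** counted if it is an AESI. Protocol 9.3.4 names gastrointestinal disorders, gastrointestinal bleeding, anemia above Grade 1 and pneumonitis for the CHHI phase. It is again not counted as an SAE.
5. **Outcome no. 5 (unsolicited AEs):** unclear. As worded in 3.2.1 it has no limit by seriousness, but Protocol 9.1 no. 5 defines unsolicited events as "non-serious adverse events occurring from the time of each study vaccination through approximately 28 days after each vaccination", with the CHHI period added on the same footing. Under 9.1, a serious hypersensitivity reaction to the larvae, for example, would not fall under this item.
6. **SAP 5.7.5.1, all-SAE table:** always counted, by group, without attribution.
7. **SAP 5.7.5.1, overview and vaccine-related SAE table:** not counted as related.
8. **SAP 5.7.5.1, by-relationship summary:** shown as related if study product has the Protocol 9.2.1 meaning, but not separable from a vaccine-related event.
9. **SAP 5.7.5.1, AE listing:** shown, with vaccine relatedness only.

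None of the nine isolates CHHI-related SAEs.

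**Illustration (hypothetical: one such event in one group).** The outcome is evaluated for each formulation against placebo, so the denominator is the group of 12. Exact (Clopper-Pearson) 95% limits:

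- Under 3.2.1: 0/12. Upper limit = 1 − 0.025^(1/12) = 1 − 0.7354 = 26.5%. Interval 0 to 26.5%.
- Under 9.1: 1/12 = 8.3%. Lower limit = 1 − 0.975^(1/12) = 0.2%. The upper limit solves (1 − p)^12 + 12p(1 − p)^11 = 0.025, giving p = 38.5%. Interval 0.2% to 38.5%.

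The intervals overlap heavily. The difference lies in whether a related SAE is reported on the primary measure at all, not in statistical precision.

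**SAE definition.** Protocol 9.2.5 counts "at least an overnight stay in the hospital or emergency ward". SAP 5.2 says "requires inpatient hospitalization or prolongation of existing hospitalization" and does not mention the emergency ward. The wordings differ, but the site classifies SAEs under the protocol and the SAP directs that it be read with the protocol, so no effect on counts is shown.

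**The case against.** The strongest reply is that this is a design choice. Primary Objective 2 concerns the vaccine formulations given on Days 0, 56 and 112. All three statements of the primary SAE outcome agree, and 9.1 lists safety parameters without calling them primary outcomes. A narrow primary item beside broader monitoring is legitimate. This stands as a possibility, but the documents do not state it, and outcomes no. 2 and no. 5 show that the primary safety set was not kept to the vaccine alone.

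The second reply is that the event is visible elsewhere and subject protection is unaffected. That is correct: the all-SAE table captures it, outcomes no. 2 and no. 7 take in many such events, and the halting rules and regulatory reporting do not depend on the outcome wording. What remains is the definition of the primary item and the lack of separate attribution.

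Three stronger readings are tempting and are not supported:

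- A reader might infer that challenge-caused SAEs are missing from the whole primary safety set. Outcomes no. 2 and no. 7 contradict that.
- A reader might infer that a placebo subject's SAE is vaccine-unrelated by definition. Allocation is blinded until after the last visit and database lock, so an investigator can grade such an event as vaccine-related.
- A reader might infer that the trial could not tell whether vaccination changes harm from the challenge. Post-CHHI events and all SAEs are tabulated by group, and a comparison between randomized groups needs no causality label.

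**Conclusion.** The concern holds in a limited form. The scope of the SAE measure differs between Protocol 9.1 and the three statements of the primary outcome. Followed as written, the plan leaves an SAE attributed only to CHHI out of the primary SAE outcome, and no planned output separates CHHI-related from vaccine-related SAEs. The data themselves are not lost.

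The size is that of a classification: any CHHI-only SAE moves from counted to not counted, illustrated by 1/12 against 0/12 in a group. The documents give no expected rate of such events, so the likelihood of this arising cannot be stated. No sample size or power figure changes.

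The conclusion assumes that investigators will attribute some events to CHHI and not to the vaccine, as 9.2.1 allows. It does not depend on the difference between the SAE definitions, which is a matter of tidying.

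**What to change.** - **Protocol 3.2.1 no. 3, Protocol 11.4 and SAP 4.1 no. 4:** reconcile with Protocol 9.1 no. 1. Either widen the item to SAEs related to study product (vaccine or CHHI), or state that the primary item is deliberately vaccine-related only and report CHHI-related SAEs alongside it.
- **SAP 5.7.5.1:** report relationship to vaccine and relationship to CHHI as two variables, by group, in the overview, the by-relationship tables and the AE listing.
- **SAP 5.2:** cross-refer to the SAE definition in Protocol 9.2.5.

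The cost is wording in both documents and one extra column in the AE tables. Protocol 9.2.1 already calls for assessment of the relationship to CHHI. The case report form is not among the documents, and Protocol 15.1 mentions only relationship to vaccination, so it should be confirmed that the form records the two relationships separately.
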